9.1.2.11. Maastricht Ankylosing Spondylitis Enthesitis Score

The Maastricht Ankylosing Spondylitis Enthesitis Score (MASES) is an index used to measure the severity of enthesitis (Hueft-Dorenbosch et al. 2003). The MASES assesses 13 sites for enthesitis using a score of “0” for no activity or “1” for activity. Sites assessed include: costochondral 1 (right/left), costochondral 7 (right/left), spinal iliaca anterior superior (right/left), crista iliaca (right/left), spina iliaca posterior (right/left), processus spinosus L5, and Achilles

tendon proximal insertion (right/left). The MASES is the sum of all site scores (range of scores: 0 to 13), higher scores indicate more severe enthesitis.

The MASES is to be assessed by a rheumatologist or health care provider who meets study qualifications for study assessment.

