Maastricht Ankylosing Spondylitis Enthesitis Score (MASES)	The MASES is an index used to measure the severity of enthesitis (Heuft-Dorenbosch et al. 2003). The MASES assesses 13 sites for enthesitis using a score of “0” for no activity, or “1” for activity. Sites assessed include: costochondral 1 (right/left), costochondral 7 (right/left), spinal iliaca anterior superior (right/left), crista iliaca (right/left), spina iliaca posterior (right/left), processus spinosus L5, and Achilles tendon proximal insertion (right/left).	MASES	The MASES is the sum of all site scores. Range: 0 to 13, higher scores indicate more severe enthesitis 0 = no activity and not evaluable 1 = activity	Missing if >20% (ie, $\geq 3$ ) sites are missing. If $\leq 20\%$ missing, then MASES score = sum of scores from nonmissing sites $\times 13/\text{no. of nonmissing sites}$ .
		MASES change from baseline	Calculated as: observed MASES – baseline MASES	Missing if baseline or observed value is missing.
		MASES = 0	Only applies to patients with baseline MASES >0 to count % of patients having MASES remission.	Missing if observed value is missing.

Spondyloarthritis Research Consortium of Canada (SPARCC) enthesitis	
SPARCC enthesitis is an index used to measure the severity of enthesitis (Maksymowich et al. 2009). The SPARCC assesses 16 sites for enthesitis using a score of “0” for no activity, or “1” for activity. Sites assessed include Medial epicondyle (left/right [L/R]), Lateral epicondyle (L/R), Supraspinatus insertion into greater tuberosity of humerus (L/R), Greater trochanter (L/R), Quadriceps insertion into superior border of patella (L/R), Patellar ligament insertion into inferior pole of patella or tibial tubercle (L/R), Achilles tendon insertion into calcaneus (L/R), and Plantar fascia insertion into calcaneus (L/R).
	SPARCC enthesitis	
The SPARCC is the sum of all site scores. Range: 0–16, higher scores indicate more severe enthesitis. SPARCC enthesitis score = 0 refers to complete resolution in enthesitis.
	Missing if >20% (ie, ≥4) sites are missing. If ≤20% missing, then imputed sum = sum of scores from nonmissing sites × 16/no. of nonmissing sites.
		SPARCC enthesitis change from baseline	Calculated as: observed SPARCC enthesitis – baseline SPARCC enthesitis.	Missing if baseline or observed value is missing.

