		SPARCC enthesitis = 0	Only applies to patients with baseline SPARCC enthesitis >0 to count % of patients having SPARCC enthesitis remission.	Missing if observed value is missing.
Tender Joint Count (TJC)	
The number of tender and painful joints will be determined by examination of 46 joints (23 joints on each side of the patient’s body). The 46 joints are assessed and classified as tender or not tender.
	TJC total score	
Adjusted sum of the pain/tenderness for all 46 joints:
 $\left( \frac{\text{sum of all joints checked to be painful/tender}}{\text{number of evaluable joints}} \right) \times 46$ 
See Appendix 2 for details.
	If more than half of the joint scores are non-evaluable, the total score will be missing.
		TJC change from baseline	Calculated as: observed TJC – baseline TJC	Missing if baseline or observed

				value is missing
		TJC = 0	only applies to patients with baseline TJC > 0 to count % of patients having TJC remission.	Missing if observed value is missing
Swollen Joint Count (SJC)	The number of swollen joints will be determined by examination of 44 joints (22 joints on each side of the patient's body). The 44 joints are assessed and classified as swollen or not swollen.	SJC total score	Adjusted sum of the pain/tenderness for all 44 joints.  $\left( \frac{\text{sum of all joints checked to be swollen}}{\text{number of evaluable joints}} \right) \times 44$  See Appendix 2 for details.	If more than half of the joint scores are not evaluable, the total score will be missing.
		SJC change from baseline	Calculated as: observed SJC – baseline SJC	Missing if baseline or observed value is missing
		SJC=0	Only applies to patients with baseline SJC > 0 to count % of patients having SJC remission..	Missing if observed value is missing
Anterior Uveitis or Uveitis Flares	Eye pain or discomfort, eye redness, blurring of vision, or any other symptoms suggestive of anterior uveitis.	Event of anterior uveitis or uveitis flare	When a patient is diagnosed as anterior uveitis or uveitis flare by an ophthalmologist (for patients with no prior history), or a physician (for patients with prior history), then the Event =1, else=0.	If missing then missing

Abbreviations: Baseline = baseline from the originating study RHBV, RHBW or RHBX; CRP = C-reactive protein; IWRS = Interactive Web Response System; no. = number; NRS = numeric rating scale; Q = question; rad-axSpA = radiographic axial spondyloarthritis.

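### MASES scores a non-evaluable site as inactive, which understates the score and can count as remission a patient with 3 or more such sites

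*SAP*

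**What the plan says.** The MASES row of SAP Table RHBY.6.4 (Section 6.10) deals with an unknown site in two places.

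- **Derivation cell.** The score is the sum over sites, with the zero code given as "0 = no activity and not evaluable".
- **Missing-components cell.** The score is missing when more than 20% of sites, that is 3 or more, are missing. Otherwise it is rescaled: "then MASES score = sum of scores from nonmissing sites", multiplied by 13 over the number of nonmissing sites.

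The description cell of the row has no non-evaluable category: "The MASES assesses 13 sites for enthesitis using a score of “0” for no activity, or “1” for activity". Protocol Section 9.1.2.11 likewise gives zero only for no activity. The SAP text does not say how a non-evaluable site differs from a missing one.

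The neighbouring rows read differently. SPARCC enthesitis has the same two-value scoring ("The SPARCC assesses 16 sites for enthesitis using a score of “0” for no activity, or “1” for activity") and the same kind of rescaling, with no clause for non-evaluable sites. The tender and swollen joint counts divide by the number of evaluable joints, and for tender joints: "If more than half of the joint scores are non-evaluable, the total score will be missing".

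MASES = 0 is a response variable: "Only applies to patients with baseline MASES >0 to count % of patients having MASES remission". Table RHBY.6.5 lists it for the RW ITT population in Period 2 (logistic regression and Fisher's exact test, both with NRI), and lists MASES change from baseline there by ANCOVA with mBOCF. Both are also summarised for the Long-Term Ixekizumab Treatment Efficacy Population.

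**The concern.** A site nobody could assess carries no information, yet the zero code enters it as evidence of no enthesitis. Once it has a value, it is no longer missing in any operational sense, so the safeguard in the next cell does not act on it. Of the four site-count and joint-count scores in this part of the table, MASES alone states that a non-evaluable location counts as inactive, and no reason is given.

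The MASES level is at stake, and so is the response classification of a patient with several non-evaluable sites. Two enthesitis indices reported side by side could also treat the same problem in different ways.

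**Working it through.** **Inputs.** 13 sites, each scored 0 or 1; zero code includes non-evaluable; rescaling and the 20% limit (all SAP Table RHBY.6.4, MASES row). A missing response is a nonresponder under NRI (SAP Section 6.3.1). Let a be the number of active sites seen and k the number of non-evaluable sites.

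**1. The plan's own threshold.** 2/13 = 15.4%, which is within 20%; 3/13 = 23.1%, which exceeds it. The stated limit of 3 reproduces.

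**2. Score level with 1 or 2 non-evaluable sites.** As coded, the score is a. Treated as missing, it is a × 13/(13 − k). The ratio of coded to rescaled is (13 − k)/13 = 1 − k/13.

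| k | shortfall of coded score | example, a = 4 |
|---|---|---|
| 1 | 1/13 = 7.7% | 4 against 4 × 13/12 = 4.33 |
| 2 | 2/13 = 15.4% | 4 against 4 × 13/11 = 4.73 |

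The coding never raises a score. If a = 0, then 0 × 13/12 = 0 and 0 × 13/11 = 0, so MASES = 0 status is the same under both rules.

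**3. Three or more non-evaluable sites.** As coded, the score is still a. Treated as missing, there is no score. With a = 0, the coded patient is in remission, whereas a missing response is a nonresponse in the RW ITT analysis. At the extreme, k = 13 gives MASES = 0 with no site evaluated.

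As an illustration, assume that non-evaluable sites fall at random and that the patient has exactly one truly active site. The chance that this site is among the k is k/13: 23.1% at k = 3, 30.8% at k = 4 and 46.2% at k = 6. Each of these patients would score zero as coded and would be missing under the row's rule.

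**4. Change from baseline.** In each case 4 active sites are seen at baseline and 2 at follow-up, so the coded change is −2.

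| Non-evaluable at baseline | Non-evaluable at follow-up | Rescaled change | Effect of coding on improvement |
|---|---|---|---|
| 0 | 2 | 2 × 13/11 − 4 = −1.64 | overstated |
| 2 | 0 | 2 − 4 × 13/11 = −2.73 | understated |
| 2 | 2 | (2 − 4) × 13/11 = −2.36 | understated |

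The direction depends on when the sites are non-evaluable.

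**The case against.** The SAP uses two terms. If non-evaluable is a recorded category and missing means no entry, both cells can operate together, and there is no outright contradiction. This stands: the conflict within the row is conditional on a definition that the SAP does not supply. It does not rescue the coding, because a recorded non-evaluable site still enters the sum as inactive.

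The comparators have limits. Protocol Sections 9.1.2.13.1 and 9.1.2.13.2 give concrete reasons for excluding joints (injected, missing, replaced, ankylosed or arthrodesed) and the protocol gives none for entheses. It is also silent on non-evaluable entheses, so the SAP adds to the protocol here and does not plainly contradict it. The SPARCC row does not mention non-evaluable sites, so any difference in their handling there is inferred.

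Three stronger readings are tempting, and the documents do not support them:

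- **That change from baseline is biased towards improvement.** Only sites that become non-evaluable after baseline push that way. The other two patterns in the working push the opposite way.
- **That any unassessed site can create remission.** With one or two, the rescaling rule also returns zero when no active site is seen. The effect specific to this coding needs three or more in one patient at one visit.
- **That the comparison with placebo is distorted.** Period 2 is randomized and double-blind (Protocol Section 7.3), and nothing in the documents suggests that non-evaluability differs by arm.

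**Conclusion.** The point holds in a limited form. As written, the zero code understates a non-zero MASES level by 7.7% with one non-evaluable site and by 15.4% with two, relative to the row's own rescaling. With three or more, it produces a number where that rule gives missing. If no examined site is active, that number counts as MASES remission instead of as an NRI nonresponse. (The rescaled score at two sites is 13/11 = 1.18 times the coded one; that is the same gap as 15.4% and does not mean the coded score is 18% too low.)

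These comparisons assume that a non-evaluable site should be handled as missing. The documents give no frequency of such sites, so the overall effect cannot be computed. The reach is confined to other secondary enthesitis endpoints in the RW ITT and long-term populations. In RW ITT these have no multiplicity adjustment (SAP Section 6.10.4); in the long-term population they are descriptive. The primary and major secondary endpoints rest on ASDAS-defined flare and are untouched.

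**What to change.** In the MASES derivation cell, remove non-evaluable from the zero code and state that a non-evaluable site is treated as missing. The existing rule then applies: rescale by 13 over the number of evaluable sites if at most 2 are non-evaluable or missing, otherwise set the score to missing. Use it for both the continuous score and MASES = 0, and identically for the originating-study baseline and for follow-up, so that the two remain comparable.

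The edit is one phrase and needs no new data collection, provided the recorded data separate non-evaluable from inactive sites. That must be checked first, including in the originating studies, whose case report forms are not part of these documents. Where both states were stored as zero, they cannot be separated afterwards, and the report should say so. One consequence to accept is that a patient with 3 or more such sites at baseline would have no baseline score and could not be placed in the subset with baseline MASES above zero.

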**Table RHBY.6.5. Description of Primary and Secondary Efficacy Analyses**

Population	Variable	Analysis Method (Section 6.1)	Comparison/Time Point
RW ITT Population (to evaluate treatment effect in maintaining response during Period 2)	For the primary and major secondary objectives: Not Flare (event: 0 or 1)	Logistic Regression analysis and with NRI; Fisher's exact test with NRI	Total IXE vs. Placebo IXE80Q2W vs. Placebo IXE80Q4W vs. Placebo at each scheduled visit in Period 2 including Week 64.
	For major secondary objectives: Time to the 1 st Flare	Kaplan-Meier product limit method Log-Rank Test	Total IXE vs. Placebo IXE80Q2W vs. Placebo IXE80Q4W vs. Placebo within Period 2 up to Week 64.
RW ITT Population (to evaluate treatment effect in achieving/maintaining response during Period 2).	For other secondary objectives: 
 
• ASDAS:               
 
Clinically-important improvement
 
Major improvement
 
Inactive disease, ASDAS <2.1
 
 
 
• ASAS20;
 
• ASAS40;
 
• ASAS5/6;
 
• ASAS partial remission,
 
• BASDAI50.
 
• Peripheral arthritis:               
 
TJC = 0 and
 
SJC = 0 for patients with TJC >0 and SJC >0, respectively, at Baseline from originating study
 
 
 
• Enthesitis: MASES = 0 and SPARCC = 0 for patients with Baseline MASES >0 and SPARCC >0, respectively.
 
 
(See Section 6.10.4 for coding for achieving/ maintaining response for these variables derived in Table RHBY.6.4)
	Logistic Regression analysis and with NRI; Fisher's exact test with NRI	Total IXE vs. Placebo IXE80Q2W vs. Placebo IXE80Q4W vs. Placebo at each scheduled visit in Period 2 including Week 64.
	Anterior uveitis or uveitis flare	Fisher's exact test and Poisson regression with total exposure adjusted	Total IXE vs. Placebo IXE80Q2W vs. Placebo IXE80Q4W vs. Placebo during Period 2

Population	Variable	Analysis Method (Section 6.1)	Comparison/Time Point
	
Change from baseline in the originating study:
 
 
ASAS - 4 components:           
 
Patient global,
 
Spinal pain,
 
Function,
 
Inflammation.
 
 
 
ASDAS
 
BASDAI,
 
BASFI,
 
BASMI:           
 
Linear,
 
Chest expansion and
 
Occiput to wall distance,
 
 
 
Enthesitis:           
 
MASES,
 
SPARCC.
 
 
 
 
For patients with MASES >0 and SPARCC >0, respectively, at baseline from originating study
 
 
Peripheral Arthritis Severity           
 
TJC
 
SJC
 
 
 
 
For patients with TJC >0 and SJC >0, respectively, at baseline from originating study
 
 
CRP
 
	ANCOVA with mBOCF	Total IXE vs. Placebo IXE80Q2W vs. Placebo IXE80Q4W vs. Placebo at each scheduled visit in Period 2 including Week 64.
Ikekizumab Structure Population (2-year radiographic progression in spine: from baseline in originating study to Week 56 in RHBY)	change in Total mSASSS 
 
Non-progressor:             
 
change in Total mSASSS <2
 
 
 
Non-progressor:             
 
change in Total mSASSS <=0
 
no new syndesmophyte
 
 
 
	Descriptive statistics	No comparisons

Population	Variable	Analysis Method (Section 6.1)	Comparison/Time Point
Long-Term Ixekizumab Treatment Efficacy Population (to evaluate long-term treatment effect through Week 104)	For other secondary objectives: • ASDAS: Clinically-important improvement, Major improvement, Inactive disease, ASDAS <2.1 • ASAS20, • ASAS40, • ASAS5/6, • ASAS partial remission, • BASDAI50. • Enthesitis: MASES = 0, SPARCC = 0. For patients with MASES >0 and SPARCC >0, respectively, at baseline from originating study • Peripheral arthritis: TJC = 0 SJC = 0 For patients with TJC >0 and SJC >0, respectively, at baseline from originating study • Anterior uveitis or uveitis flare: Crude and exposure-adjusted incidence rates for patients with anterior uveitis	Descriptive statistics (for categorical variables with observed and mNRI through Week 104)	IXE80Q2W a IXE80Q4W a Total IXE at each scheduled visit from Week 0 in originating study to Week 64 and Week 104, respectively.
Long-Term Ixekizumab Treatment Efficacy Population (to evaluate long-term treatment effect through Week 64 and Week 104, respectively)	For other secondary objectives: Change from Baseline for: • ASAS - 4 components: Patient global, Spinal pain, Function, Inflammation. • ASDAS • BASDAI, • BASFI,	Descriptive statistics (for continuous variables with mBOCF and MMRM through Week 104)	IXE80Q2W a IXE80Q4W a Total IXE a at each scheduled visit from Week 0 in originating study to Week 64 and Week 104, respectively.

Population	Variable	Analysis Method (Section 6.1)	Comparison/Time Point
	
 
BASMI:           
 
Linear,
 
Chest expansion and
 
Occiput to wall distance,
 
 
 
Enthesitis:           
 
MASES,
 
SPARCC.
 
 
 
 
For patients with MASES >0 and SPARCC >0, respectively, at baseline from originating study
 
 
Peripheral Arthritis Severity           
 
TJC
 
SJC
 
 
 
 
For patients with TJC >0 and SJC >0, respectively, at baseline from originating study
 
 
CRP
 
		
	
Other secondary outcomes:
 
Treatment group by TE-ADA, NAb and Titer group on:
 
 
ASAS20,
 
ASAS40,
 
ASDAS <2.1
 
	
Descriptive statistics (observed):
 
Number and proportion of patients achieving response of interest.
 
No inferential statistics.
	
IXE80Q2W, IXE80Q4W, Total IXE by TE-ADA status, NAb status, and titer group, respectively. At Week 64 and Week 104

Flare Population with Retreatment (to assess the efficacy of retreatment)
	
For other secondary objectives:
 
 
ASAS20,
 
ASAS40,
 
ASAS5/6,
 
ASAS partial remission,
 
ASDAS:           
 
ASDAS<1.3
 
ASDAS<2.1
 
 
 
Clinically-important improvement
 
Major improvement,
 
Inactive disease
 
	
Descriptive statistics (for categorical variables) for within 16 weeks of ixekizumab retreatment.
 
Kaplan-Meier estimates of the proportion of patient who regain response on the variables of interest at each post-retreatment interval up to 40 weeks.
	
PBO/IXE80Q2W, PBO/IXE80Q4W PBO/IXE IXE80Q2W/ IXE80Q2W IXE80Q4W/ IXE80Q4W IXE/IXE
 
no inferential statistics within 16 weeks of Ixekizumab retreatment and at each retreatment interval (4 weeks, 8 weeks, etc.) up to 40 weeks.

Abbreviations: ASAS = Assessment of Spondyloarthritis International Society; ASDAS = Ankylosing Spondylitis Disease Activity Score; BASDAI = Bath Ankylosing Spondylitis Disease Activity Index; BASFI = Bath Ankylosing Spondylitis Functional Index; BASMI = Bath Ankylosing Spondylitis Metrology Index; Baseline=baseline from the originating study RHBV, RHBW or RHBX; CRP = C-reactive protein; ITT = intent-to-treat; IXE-Structure = patients from Ixekizumab Structure Population; IXE80Q2W = ixekizumab 80 mg every 2 weeks; IXE80Q4W = ixekizumab 80 mg every 4 weeks; MASES = Maastricht Ankylosing Spondylitis Enthesitis Score; mBOCF = modified baseline observation carried forward; MMRM = mixed model for repeated measures; mNRI = modified nonresponder imputation; NRI = nonresponder imputation; SJC = swollen joint count; TJC = tender joint count; Total IXE = IXE80Q2W and IXE80Q4W combined; RW = randomized withdrawal.

a— IXEQ2W is a group of patients who have been treated consistently with ixekizumab 80 mg every 2 weeks since Week 0 in the originating studies through Week 64 of RHY. IXEQ4W is a group of patients who have been treated consistently with ixekizumab 80 mg every 4 weeks since Week 0 in the originating studies through Week 64 of RHY.

### **6.10.1. Primary Outcome and Methodology**

The primary outcome to test whether the Combined Ixekizumab treatment group is superior to the placebo group in maintaining response during the RWR Period (Period 2) as measured by the proportion of patients in the RW ITT Population who do not experience a flare during the RWR Period (Period 2).

Although it is expected to be very rare that a patient, who has met the sustained remission criteria at Weeks 16 and 20 and is randomized at Week 24, will have ASDAS score  $>3.5$  or  $\geq 2.1$  at Week 24 (V505), for purpose of retreatment, V505 will however be included for assessment of flare in the IWRS. However, for statistical analysis, V505 will not be included for assessment of flare, because it is before the randomized-withdrawal. According to ITT principle, all patients will be included for the efficacy analysis with an assumption that all patients will have no flare at Week 24 at time of initiation of the randomized-withdrawal. The potential bias caused by the violation of the assumption will be justified by the randomization and will be minimal. The general rule will be applied for the retreatment: A patient is considered as non-responder if the patient is retreated (see Section 6.1), namely, Flare=1.

The primary analysis is a logistic regression analysis with treatment group, geographic region (Europe versus Non-Europe) and originating study in the model (Section 6.1.3.1). Missing data will be imputed using the NRI method (Section 6.3.2).

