### ***6.1.3. General Considerations for Analyses during the Extension Period Including the Double-Blind RW Period (Period 2)***

#### **6.1.3.1. RW ITT and RW Safety Populations**

For patients who are randomized in Period 2 (group B), comparisons between Combined Ixekizumab treatment group and placebo, as well as between each ixekizumab regimen (80 mg Q2W or 80 mg Q4W) and placebo, will be performed for all analyses at each scheduled visit in Period 2 including Visit 515 at Week 64.

Period 2 starts at the first injection of study treatment after randomization (at Week 24) and ends at the following study events:

- Prior to the first injection of study treatment at Week 64 (Visit 515) for not retreated patients who have completed visit at Week 64. If injection at Week 64 is missing, the next injection date after Week 64 is used;
- Prior to the first injection of retreatment for patients who have been retreated within Period 2;
- ETV prior to Week 64.

For patients who are in the RW ITT Population and have been retreated with the ixekizumab treatment regimen due to a flare or any other reasons, only data prior to the time of the retreatment will be included in the analysis for Period 2. Data after retreatment will be imputed using nonresponder imputation (NRI) method for categorical variables and mBOCF method for continuous variables.

The observed values after retreatment will be used for other specified analysis, for example, efficacy analysis for Flare Population with Retreatment.

For efficacy and health outcomes, baseline is defined as the last available value before the first dose of study treatment in Period 2 from the originating study and, in most cases, will be the value recorded at Week 0 from the originating study.

The primary analysis method for treatment comparisons of categorical binary efficacy and health outcome variables will be a logistic regression with treatment group, geographic region, and originating study as factors using PROC Logistic with Wald method. The odds ratio and 95% CIs will be reported; treatment difference and 95% CI will also be reported. In the case when logistic regression model does not produce statistical results due to sparse data, Fisher's exact test will be used. Same analysis will also be carried out at each of other scheduled visits in Period 2.

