The Kaplan-Meier product limit method will be used to estimate the survival curves for time (from Week 24 in RHBY) to flare. The number of patients at risk and experiencing flare by each scheduled visit during Period 2 will be presented by treatment group. The Kaplan-Meier estimate of the proportion of patients experiencing flare will be presented for each scheduled visit. Treatment group comparisons will be performed using the log-rank test with strata of geographic region and originating study. A Kaplan-Meier plot of time to the first flare by treatment group will also be provided.

Time to the first flare is defined as:

$$\begin{aligned} \text{Time to the first flare (weeks)} &= (\text{Date of the first flare during the analysis period} \\ &\quad - \text{Date of the randomization at Week 24} + 1)/7 \end{aligned}$$

Patients completing the treatment period without flare will be censored at the date of completion of the analysis period (eg, for Period 2, it is the date of Week 64 injection, or the last scheduled visit in the period if Week 64 injection date is missing). Patients without flare and a date of treatment period completion or a date of discontinuation will be censored at date of last dose in

the treatment period or date of last attended visit in the treatment period (scheduled or unscheduled), whichever is later.

Figures showing the proportion of patients not-experiencing flare at each scheduled visit within each treatment group will be provided. Figures showing the proportion of patients with ASAS20, ASAS40, ASAS partial remission, BASDAI50 and ASDAS inactive disease at each scheduled visit within each treatment group may also be provided.

The primary analyses for the continuous efficacy and health outcomes variables (see derivation in Sections 6.10.4 and 6.11) will be analyzed using analysis of covariance (ANCOVA) with mBOCF for missing data. The model will include treatment, Week 24 value, baseline value, geographic region, and originating study. Type III sums of squares for the LS means will be used for the statistical comparison; the 95% CI will also be reported.

For variables that are not collected at each postrandomization visit due to early discontinuation visits, data may exist at visits where the variable is not scheduled to be collected. Such data will be used in shift analyses, change from baseline to mBOCF endpoint analyses and other categorical analyses for the RW ITT and Safety Populations.

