For safety analysis for the RW Safety Population, baseline is defined as the last nonmissing assessment prior to the first injection of study treatment in Period 2.

Fisher's exact test will be used for all adverse event (AE), discontinuation, and other categorical safety data. Continuous vital sign and laboratory values will be analyzed by an ANCOVA with treatment and baseline value in the model.

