## **6.2. Adjustments for Covariates**

The randomization to treatment groups in Period 2 is stratified by geographic region ([Table RHBY.6.2](#)) and originating study (ie, RHBV, RHBW, and RHBX) as described in Protocol Section 6.2. The geographic regions will be collapsed into 2 levels, Europe versus Non-Europe, for statistical analysis ([Table RHBY.6.3](#)). Unless otherwise specified, all efficacy and health outcomes analysis during Period 2 for the RW ITT population will include geographic region and originating study in the analysis model. In general, when ANCOVA is used for analyses during Period 2 for the RW ITT population, baseline value and Week 24 value will be included as covariates.

The initial country allocations and geographic region classification for countries is shown in [Table RHBY.6.2](#).

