### **6.10.2. Major Secondary Efficacy Analysis**

The major secondary outcomes are:

- To evaluate in patients having achieved a state of sustained remission whether ixekizumab 80 mg every 4 weeks (Q4W) treatment group is superior to placebo in maintaining response as measured by the proportion of patients in the randomized-withdrawal population who do not experience a flare during the randomized withdrawal-retreatment period
- To evaluate in patients having achieved a state of sustained remission whether the Combined Ixekizumab treatment group is superior to the placebo group in maintaining response after treatment withdrawal as measured by the time to the first flare during the randomized withdrawal-retreatment period
- To evaluate in patients having achieved a state of sustained remission whether the ixekizumab 80 mg Q4W treatment group is superior to placebo in maintaining response after treatment withdrawal as measured by the time to the first flare during the randomized withdrawal-retreatment period.

The primary analysis for categorical major secondary outcomes is a logistic regression analysis with treatment, geographic region, and originating study will be included in the model (Section 6.1.3.1). In the case when logistic regression model does not produce statistical results due to sparse data, Fisher's exact test will be used. Missing data will be imputed using the NRI method (Section 6.3.2).

Kaplan-Meier product limit method will be used to estimate the survival curves for time to the first flare for patients in RW ITT Population during Period 2. The number of patients at risk and experiencing flare by each scheduled visit during Period 2 will be presented by treatment group. The Kaplan-Meier estimate of the proportion of patients experiencing flare will be presented for each visit. Treatment group comparisons will be performed using the log-rank test with strata of geographic region and originating study. A Kaplan-Meier plot of time to the first flare by treatment group will also be provided. See Section 6.1.3 for censored data.

The variable derivations for the major secondary outcomes are described in [Table RHBY.6.4](#).

The treatment group comparisons for the primary and major secondary outcomes will be tested based on the graphical multiple testing procedure detailed in Section 6.5.

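### The primary and Q4W flare models could adjust for Week 24 ASDAS, a cheap gain in robustness that the plan leaves unused

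*SAP*

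**What the plan says.** SAP 6.1.3.1 sets the general Period 2 model for binary outcomes as "logistic regression with treatment group, geographic region, and originating study as factors using PROC Logistic with Wald method". SAP 6.10.1 applies it to the primary comparison, Total IXE against placebo: "The primary analysis is a logistic regression analysis with treatment group, geographic region (Europe versus Non-Europe) and originating study in the model". SAP 6.10.2 applies it to the Q4W comparison: "logistic regression analysis with treatment, geographic region, and originating study will be included in the model". No disease-activity term appears in any of the three.

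Continuous efficacy and health outcomes in the same population are handled differently. SAP 6.1.3.1 says "The model will include treatment, Week 24 value, baseline value, geographic region, and originating study", and SAP 6.2 states as a general rule for ANCOVA that "baseline value and Week 24 value will be included as covariates". Period 2 safety ANCOVAs are simpler: "Continuous vital sign and laboratory values will be analyzed by an ANCOVA with treatment and baseline value in the model".

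ASDAS is measured at Week 24 (V505), since "V505 will however be included for assessment of flare in the IWRS". The analysis itself excludes that visit from the endpoint: "for statistical analysis, V505 will not be included for assessment of flare". SAP 6.10.1 expects a raised ASDAS at Week 24 to be very rare and relies on randomisation to make any resulting bias minimal.

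**The concern.** Flare is an ASDAS threshold event: at least 2.1 at two consecutive visits, or above 3.5 once (SAP Table RHBY.6.4). Week 24 ASDAS fixes how far each patient stands from that threshold when treatment is withdrawn, so it is a natural candidate for a prognostic covariate. There is also a direct link to the endpoint. The IWRS counts V505 when it triggers retreatment, and SAP 6.10.1 codes any retreated patient as a flare. A patient at 2.1 or more at V505 therefore needs only one further raised visit, where others need two.

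Randomisation is stratified by region and originating study within each dose group, so nothing in the design balances Week 24 disease activity. The Week 24 ASDAS value adjusts ASDAS when it is analysed as a continuous outcome, but not when it is analysed as the primary endpoint. The documents give no reason for the difference.

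At stake are power and robustness to chance imbalance if the true flare rates are closer than planned. SAP 6.5 tests in a fixed order and the two flare proportions come first, so a failed flare test blocks every test after it.

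**Working it through.** **Inputs from the documents (SAP 5.2, Protocol 10.1).** Total 200 patients, about 100 per dose, randomised 2:1, giving about 133 ixekizumab and 67 placebo. Flare rates 10% and 70%. Two-sided alpha 0.05, Fisher's exact test. Fallback of about 150 patients (100 and 50). For Q4W the documents do not say whether placebo is pooled or only the Q4W-origin patients, so both 67 v 67 and 67 v 33 are shown.

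**Step 1: the plan's own figure.** Exact Fisher power, summed over both binomial distributions at 10% and 70%, exceeds 99.99% at 133 v 67 and at 100 v 50. The stated figures, over 99% and over 95%, both hold. Q4W gives 100.00% (67 v 67) or 99.999% (67 v 33).

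**Step 2: models compared.**
- Plan: logit P(flare) = a + b·treatment + region + study.
- Alternative: the same, plus g·z, where z stands for standardised Week 24 ASDAS and g = ln(odds ratio per SD).

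The documents do not give the strength of g. It was assumed, at odds ratios of 1, 1.5, 2 and 3 per SD. There were 2,000 simulated trials per setting, with a normally distributed covariate and Wald tests. The standardised risk difference is the average over all patients of the predicted risk on ixekizumab minus the predicted risk on placebo.

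**Step 3: planned rates, 10% v 70%.** Power is 100.0% under both models for all three comparisons. For the combined test:

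| Odds ratio per SD | SE of log odds ratio, plan → adjusted | Fall in variance of standardised risk difference |
|---|---|---|
| 1.5 | about 0.42 → 0.44 | about 2% |
| 2 | about 0.42 → 0.48 | about 6% |
| 3 | about 0.42 → 0.54 | about 15% |

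**Step 4: rates closer than planned, 30% v 50% (assumed).**

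| Comparison | Odds ratio 2 per SD | Odds ratio 3 per SD |
|---|---|---|
| Combined, 133 v 67 | 78.7% → 82.9% | 78.0% → 86.1% |
| Q4W v pooled placebo, 67 v 67 | 66.2% → 68.8% | 65.7% → 73.4% |
| Q4W v own placebo, 67 v 33 | 49.3% → 52.9% | 50.0% → 57.2% |

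The gains run from 2.6 points (68.8 − 66.2) to 8.1 points (86.1 − 78.0). At an odds ratio of 1 per SD the combined figures are 79.2% and 79.0%, so there is no gain. Simulation error on a power near 80% is √(0.8 × 0.2 / 2000) = 0.9 points.

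Power rises although the standard error rises, because the conditional log odds ratio moves further from zero. For the combined test at an odds ratio of 2 per SD, the typical Wald ratio goes from 0.87/0.317 = 2.74 to 0.97/0.338 = 2.87. At 3 per SD it goes from 0.88/0.317 = 2.78 to 1.09/0.363 = 3.00.

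At 20% v 50% and an odds ratio of 2 per SD, the combined test moves only from 98.8% to 99.4%.

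**Step 5: chance imbalance.** Take the fifth of simulated trials in which ixekizumab drew the higher Week 24 values (mean excess 0.2 to 0.3 SD), at an odds ratio of 2 per SD. Power was 57% unadjusted and 71% adjusted for 150 patients at 20% v 40%. It was 58% and 74% for Q4W at 67 v 33 and 20% v 45%. These rates are also assumptions.

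**The case against.** The strongest reply is that nothing is broken. The model matches Protocol 10.3.1.2.1 and adjusts for the two stratification factors, which is an accepted prespecified choice. At the design rates there is no power to gain. Every gain above rests on flare rates and a covariate strength that appear nowhere in the documents. Entry required ASDAS below 2.1 at Weeks 16 and 20 and below 1.3 at one of them, and the score has a floor of 0.6361. Week 24 values are therefore probably compressed, less spread than the simulated normal covariate, which would limit prognostic strength. All of this stands. It sets the size of the point but does not remove it, because the covariate is already collected and adjusting for it costs almost nothing.

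Three stronger readings are tempting, and the documents support none of them.

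- A reader might infer that Week 24 ASDAS is already in every Period 2 ANCOVA and was singled out for omission here. The natural reading of the SAP is each efficacy variable's own Week 24 value, under a rule stated in general terms. Week 24 ASDAS then enters only the ASDAS ANCOVA, and the safety ANCOVAs carry no such term.
- A reader might infer that adjustment sharpens the odds ratio at no cost. In a logistic model the standard error of the log odds ratio rises and the odds ratio changes meaning. The gain lies in power and in a standardised risk difference.
- A reader might infer that the handling of V505 biases the primary test. Week 24 status precedes the randomised treatment and the rule is the same in both arms, so randomisation balances it in expectation. Only chance imbalance remains.

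**Conclusion.** The omission is plain in SAP 6.1.3.1, 6.10.1 and 6.10.2. Its consequence is small: the planned test is valid, and no power figure in the documents changes. The case for adjusting is insurance. It matters only if Week 24 ASDAS predicts flare and the true rates turn out much closer than 10% and 70%. The variance range of about 2% to 15% is for the combined comparison at planned rates with odds ratios of 1.5 to 3 per SD. The power range of roughly 3 to 8 points is for 30% v 50% with odds ratios of 2 to 3 per SD. Both are conditional on those assumptions, and both shrink to nothing if the covariate is not prognostic.

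**What to change.** Before unblinding, amend SAP 6.1.3.1, 6.10.1 and 6.10.2 so that the logistic models for flare (Total IXE v placebo and Q4W v placebo) include Week 24 ASDAS as a continuous covariate. If a component is missing at Week 24, use the carry-forward rule already in Table RHBY.6.4. SAP 6.1.3.1 promises a treatment difference with a 95% CI but names no method. State that both are obtained by standardisation from this model. Keep the existing Fisher fallback for sparse data. The time-to-flare tests are unaffected.

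The cost is one extra model term and no new data. The odds ratio becomes conditional on Week 24 ASDAS and its log-scale standard error rises, so retain the model without ASDAS as a sensitivity analysis in SAP 6.10.3. If the sponsor prefers not to alter the primary model, the minimum is to prespecify the adjusted model there instead.
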